4.2.2.2 Dinaciclib

Dinaciclib was rapidly eliminated from plasma; mean terminal phase half-life values ranged from 2 to 3 hours. There was a dose-related increase in exposure with doses from 0.33 to 58 mg/m². Dinaciclib did not accumulate in plasma upon weekly or Q3W multiple dosing. Coadministration of dinaciclib with aprepitant, an antiemetic agent, did not affect the pharmacokinetics of dinaciclib.

Phase 1 dose-escalation trials investigating two different IV dosing schedules of dinaciclib have determined the maximum administered dose and the RPTD for each schedule. Safety and PK data from these trials support the doses selected for further evaluation of dinaciclib. In the first Phase 1 trial (PN001), dinaciclib was administered as a 2-hour IV infusion on Days 1, 8, and 15 of a 28-day cycle to subjects with advanced malignancy refractory to conventional treatment. In subjects with solid tumors, a maximum administered dose of 14 mg/m² was reached in the PN001 trial, with an RPTD of 12 mg/m². The trial included an expansion cohort, at the RPTD of 12 mg/m², exploring safety and tolerability in subjects with MM or NHL. In Arm B of the PN001 trial, dose exploration to minimize the incidence of tumor lysis syndrome (TLS) in subjects with CLL revealed an RPTD of 7>10>14 mg/m² (Days 1, 8, and 15, respectively) in Cycle 1 and 14 mg/m² in Cycle 2 and thereafter (28-day cycles).

A Phase 1 trial examining dinaciclib administered as a 2-hour IV infusion given Q3W in a similar subject population (PN002) has determined an RPTD of 50 mg/m². In the acute leukemia trial (PN005), a planned safety analysis of intrasubject dose escalation from dinaciclib at 50 mg/m² to 70 mg/m², starting in Cycle 2, concluded that the 70 mg/m² dose is safe.

4.2.3 Rationale for Endpoints

4.2.3.1 Efficacy Endpoints

The primary efficacy objective for both arms of this trial is to evaluate the antitumor activity of pembrolizumab in combination with dinaciclib in subjects with rrCLL, rrMM, or rrDLBCL. The primary efficacy endpoint will be ORR as assessed by the investigator, according to tumor-specific response criteria. Objective response rate is an acceptable measure of clinical benefit to demonstrate a new antineoplastic combination therapy.

Other secondary efficacy endpoints will include DOR, PFS, and OS. These endpoints are commonly accepted endpoints by both regulatory authorities and the oncology community.

4.2.3.2 Safety Endpoints

The safety and tolerability of pembrolizumab in combination with dinaciclib in subjects with rrCLL, rrMM, or rrDLBCL will be characterized in this trial. The safety analysis will be based on subjects who experienced toxicities as defined by Common Toxicity Criteria for Adverse Events (CTCAE). Safety will be assessed by quantifying the toxicities and grades experienced by subjects who have received pembrolizumab in combination with dinaciclib, including serious adverse events (SAEs) and events of clinical interest (ECIs).

Safety will be assessed by reported AEs using CTCAE, Version 4.0. The attribution to drug, time-of-onset, duration of the event, its resolution, and any concomitant medications administered will be recorded. AEs will be analyzed including but not limited to all AEs, SAEs, fatal AEs, and laboratory changes.

4.2.3.3 Pharmacokinetic Endpoints

The PK endpoints of this trial are to define:

- the plasma concentration profile and estimate dinaciclib exposure following a 2-hour IV infusion, and
- the plasma concentration profile of pembrolizumab exposure following administration of combination therapy.

Plasma concentrations of dinaciclib and pembrolizumab will be determined using validated high performance liquid chromatography-tandem mass spectrometry methods.

Plasma drug concentration versus time data collected for PK purposes will be analyzed. Additionally, correlations between the model-estimated drug exposure and other subject characteristics, such as concomitant medication, available AEs, or pharmacodynamic data, may be explored.

4.2.3.4 Planned Exploratory Biomarker Research

Biomarker research to identify factors important for pembrolizumab therapy may be pursued. For example, pre- and post-dose bone marrow biopsies, lymph node biopsies, and blood samples from this trial may undergo flow cytometric, proteomic, genomic, and transcriptional analyses at a central laboratory. Lymph node biopsies, bone marrow aspirates, saliva, and/or blood samples will be evaluated using DNA sequencing. Using both pre- and post-treatment tumor biopsies and/or blood samples (serum or plasma), change in baseline of candidate biomarkers may also be assessed using Nanostring/ RNAseq for gene expression.

Additional research may evaluate factors important for predicting responsiveness or resistance to pembrolizumab or dinaciclib therapy and other immunologic targets. In addition, biomarker assay characterization may be performed to evaluate factors important for the identification of biomarkers.

Assays may include but are not be limited to:

Multiplex Flow Cytometric Analysis

Emerging data suggest that blockade of the PD-1/PD-L1 pathway results in enhanced T-cell mediated immune response. To test the hypothesis that T-cell activation mediated by pembrolizumab treatment correlates with clinical response, total T-cell count and T-cell subsets in peripheral blood, eg, naïve, activated, memory, and regulatory T cells, will be assessed pre- and post-dose and in both responders and non-responders. Natural killer cells enumeration will also be performed pre- and post-dose in both responders and non-responders.

Transcriptional Analyses

mRNA expression profiling in archival material, lymph node samples, and blood samples will be completed to assess gene expression and to attempt to define a gene set critical for clinical response to pembrolizumab. The hypothesis to be tested is that pembrolizumab responders will exhibit a “stalled Cytotoxic T Lymphocyte” response within the tumor reflected in the physical proximity between PD-1 and PD-L1 expression and the presence of an aborted (eg, weak but discernible) interferon-gamma transcriptional program will be detectable by profiling analyses. Global profiling will also be pursued.

Expression of individual genes related to the immune system may also be evaluated such as immune signatures and critical cytokines (eg, interleukin-10).

Gene Sequencing

New data are emerging that suggest we can define certain tumor types as having high mutational burden. There is a potential that this hypermutated state may correlate with response to pembrolizumab therapy, and/or that the converse, ‘hypomutated’ state may correlate with non-response.

Genome-wide whole exome sequencing may be performed from archival material, lymph node samples, and blood samples to assess genomic events such as but not limited to mutational burden as well as to evaluate fusion and amplification events such as 9p24.1 amplification.

Planned Genetic Analysis

Understanding genetic determinants of drug response is an important endeavor during medical research. This research will evaluate whether genetic variation within a clinical trial population correlates with response to the treatment(s) under evaluation. If genetic variation is found to predict efficacy or AEs, the data might inform optimal use of therapies in the subject population. This research contributes to understanding genetic determinants of efficacy and safety associated with the treatments in this trial.

Anti-Pembrolizumab Antibodies

Formation of antidrug antibodies (ADAs) can potentially confound drug exposures at therapeutic doses, and prime for subsequent infusion-related toxicities. Incidence of ADAs and neutralizing ADAs will be evaluated. Correlations between the presence/absence in subjects of ADAs with PK and pharmacodynamic markers, activity, and safety of pembrolizumab may be explored.

4.2.3.5 Future Biomedical Research

The Sponsor will conduct Future Biomedical Research on specimens collected for future biomedical research during this clinical trial. This research may include genetic analyses (DNA), gene expression profiling (RNA), proteomics, metabolomics (serum, plasma) and/or the measurement of other analytes.

Such research is for biomarker testing to address emergent questions not described elsewhere in the protocol (as part of the main trial) and will only be conducted on specimens from appropriately consented subjects. The objective of collecting specimens for Future Biomedical Research is to explore and identify biomarkers that inform the scientific

understanding of diseases and/or their therapeutic treatments. The overarching goal is to use such information to develop safer, more effective drugs/vaccines, and/or to ensure that subjects receive the correct dose of the correct drug/vaccine at the correct time. The details of Future Biomedical Research are presented in Section 12.2 - Collection and Management of Specimens for Future Biomedical Research. Additional informational material for institutional review boards/ethics committees (IRBs/ERCs) and investigational site staff is provided in Section 12.3.

4.3 Benefit/Risk

Subjects in clinical trials generally cannot expect to receive direct benefit from treatment during participation, as clinical trials are designed to provide information about the safety and effectiveness of an investigational medicine.

Preclinical and clinical data for pembrolizumab and dinaciclib have demonstrated antitumor activity in various tumor types, including hematologic malignancies. Enhanced antitumor activity was observed with the combination of pembrolizumab and dinaciclib in preclinical studies using a solid tumor syngeneic model (MC38). There were no significant safety findings with the combination. Based on the available preclinical and clinical information, the benefit/risk of the pembrolizumab plus dinaciclib combination appears reasonable to evaluate in a Phase Ib clinical trial.

Additional details regarding specific benefits and risks for subjects participating in this clinical trial may be found in the accompanying IBs and informed consent documents.

5.0 METHODOLOGY

5.1 Entry Criteria

5.1.1 Diagnosis/Condition for Entry into the Trial

Male/Female subjects who are at least 18 years of age on the day of signing informed consent with histologically confirmed diagnosis of rrCLL, rrMM, or rrDLBCL will be enrolled in this trial.

5.1.2 Subject Inclusion Criteria

In order to be eligible for participation in this trial, the subject must:

All Subjects:

1. Be willing and able to provide written informed consent/assent for the trial. The subject may also provide consent/assent for Future Biomedical Research. However, the subject may participate in the main trial without participating in Future Biomedical Research.
2. Be \geq 18 years of age on day of signing informed consent.
3. Female subjects of childbearing potential should have a negative urine or serum pregnancy within 72 hours prior to receiving the first dose of trial medication. If the urine test is positive or cannot be confirmed as negative, a serum pregnancy test will be required.

4. Female subjects of childbearing potential must be willing to use an adequate method of contraception as outlined in Section 5.7.2 - Contraception, for the course of the trial through 120 days after the last dose of trial medication.

Note: Abstinence is acceptable if this is the usual lifestyle and preferred contraception for the subject.

5. Male subjects of childbearing potential must agree to use an adequate method of contraception as outlined in Section 5.7.2 - Contraception, starting with the first dose of trial therapy through 120 days after the last dose of trial therapy.

Note: Abstinence is acceptable if this is the usual lifestyle and preferred contraception for the subject.

6. Must have a performance status of 0 or 1 on the Eastern Cooperative Oncology Group (ECOG) Performance Scale.
7. Cardiac function suitable for hydration guidelines outlined in [Table 6](#) and [Table 7](#) per investigator and/or cardiologist.
8. Be able to provide newly obtained (within 3 months) bone marrow biopsy material for biomarker analysis. If bone marrow biopsy was performed within 3 months before screening but subject had anticancer treatment after biopsy, the bone marrow biopsy and aspiration should be repeated.

9. Must demonstrate adequate organ function as defined below (Table 1):

Table 1 Subject Inclusion Criteria - Adequate Organ Function

System	Laboratory Value
Hematological	
ANC	> 1,500/ μ L (unless due to marrow involvement)
Platelets ^a	\geq 100,000/ μ L (\geq 30,000/ μ L for CLL)
Hemoglobin ^a	\geq 8.0 g/dL or \geq 1.24 mmol/L ^a
Renal	
Creatinine OR	\leq 1.5 X ULN OR
Measured or calculated ^b creatinine clearance (GFR can also be used in place of creatinine or creatinine clearance)	\geq 60.0 mL/min for subject with creatinine levels > 1.5 X institutional ULN
Hepatic	
Total bilirubin	\leq 1.5 X ULN OR
	Direct bilirubin \leq ULN for subjects with total bilirubin levels > 1.5 ULN
AST and ALT	\leq 2.5 X ULN OR \leq 5 X ULN for subjects with liver metastases
Coagulation	
INR or PT aPTT	\leq 1.5 X ULN unless subject is receiving anticoagulant therapy as long as PT or PTT is within therapeutic range of intended use of anticoagulants
Abbreviations: ALT (SGPT) = alanine aminotransferase (serum glutamic pyruvic transaminase); ANC = absolute neutrophil count; aPTT = activated partial thromboplastin time; AST (SGOT) = aspartate aminotransferase (serum glutamic oxaloacetic transaminase); CLL = chronic lymphocytic leukemia; GFR=glomerular filtration rate; INR = international normalized ratio; PT = prothrombin time; PTT = partial thromboplastin time; ULN=upper limit of normal. ^a Criteria must be met without erythropoietin dependency and without packed red blood cell (pRBC) transfusion within last 2 weeks. ^b Creatinine clearance should be calculated per institutional standard. Note: This table includes eligibility-defining laboratory value requirements for treatment; laboratory value requirements should be adapted according to local regulations and guidelines for the administration of specific chemotherapies.	

CLL –Note: The rrCLL cohort was closed to enrollment on 30-APR-2019 due to lack of accrual, and all subjects with rrCLL have discontinued from treatment. Remaining subjects with rrCLL are in survival follow-up.

10. Confirmed diagnosis of CLL as defined by 2008 iwCLL criteria.

11. Subjects must have received at least one prior therapy.

12. Must meet one or more of the following consensus criteria for initiating treatment:

- Progressive disease or marked splenomegaly and/or lymphadenopathy,
- Anemia (hemoglobin < 11 g/dL) or thrombocytopenia (platelets < 100,000/mm³),
- Unexplained weight loss \geq 10% of body weight over preceding 6 months
- National Cancer Institute CTCAE Grade 2 or 3 fatigue,

- Fevers >100°F/38°C or night sweats for greater than 2 weeks without evidence of infection,
- Progressive lymphocytosis, with an increase > 50% over a 2-month period or a doubling time < 6 months.

MM - Note: The rrMM cohort was closed to enrollment on 07-AUG-2017 due to lack of efficacy, and all subjects discontinued from treatment.

13. Has a confirmed diagnosis of active MM and measurable disease defined as:

- Serum monoclonal protein (M-protein) levels ≥ 0.5 g/dL or
- Urine monoclonal protein (M-protein) levels ≥ 200 mg/24-hrs or
- For subjects without measurable serum and urine M-protein levels, an abnormal serum free light chain ratio (FLC k/l) with involved FLC level ≥ 100 mg/L. (Normal serum FLC k/l value: 0.26-1.65).

14. Must have undergone prior treatment with ≥ 2 treatment lines of anti-myeloma therapy and must have failed their last line of treatment defined as documented disease progression during or within 60 days of completing their last anti-myeloma therapy (refractory to last line of treatment)

15. Prior anti-myeloma treatments must have included an IMiD (pomalidomide, lenalidomide, or thalidomide) AND proteasome inhibitor (bortezomib, carfilzomib, or ixazomib) alone or in combination and subject must have failed therapy with an IMiD OR proteasome inhibitor defined as one of the following:

- Refractory: Documented progressive disease on or within 60 days of completing treatment with an IMiD and/or proteasome inhibitor OR
- Relapsed and refractory: In case of prior response (\geq PR) to an IMiD or proteasome inhibitor, subjects must have relapsed within 6 months after stopping treatment with an IMiD and/or proteasome inhibitor-containing regimens.

DLBCL

16. Has a histologically confirmed diagnosis of DLBCL.

17. Subjects must have progressed following at least 2 lines of previous therapy, including progression after an autologous stem cell transplant (SCT), or are not a candidate (per institutional criteria) for an autologous stem cell transplant. Subjects who are ineligible for standard treatment or who have withdrawn from standard treatment due to unacceptable toxicity warranting discontinuation of that treatment and precluding retreatment with the same agent before progression of disease will also be eligible.

18. Have measurable disease, defined as at least one lesion that can be accurately measured in at least 2 dimensions with spiral computed tomography (CT) scan. Minimum measurement must be > 15 mm in the longest diameter or > 10 mm in the short axis.

19. Be able to provide newly obtained (within 3 months) core or excisional biopsy from lymph node or extranodal location for biomarker analysis. If bone marrow biopsy was performed 3 months before screening but subject had anti-cancer treatment after biopsy, the bone marrow biopsy and aspiration should be repeated.

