7.1.3.1 Laboratory Safety Evaluations (Hematology, Chemistry and Urinalysis)

Laboratory tests for hematology, chemistry, and urinalysis are specified in [Table 16](#). Except for analyses of biomarkers or other prognostic indicators (proteomics, genetics, transcriptional analysis, pharmacokinetics, antibodies), all tests will be analyzed locally.

Table 16 Laboratory Tests

Hematology	Chemistry	Urinalysis	Other
Hematocrit	Albumin	Blood	Pregnancy test (serum or urine) ^a
Hemoglobin	Alkaline phosphatase	Glucose	PT/INR
Platelet count	Alanine aminotransferase	Protein	aPTT
WBC (total and differential) ^d	Aspartate aminotransferase	Specific gravity	Total T3 or free T3, FT4, and TSH ^b
RBC	Bicarbonate ^c	Microscopic exam, if abnormal results are noted	B2 microglobulin G6PD (as necessary)
Absolute lymphocyte count ^d	Calcium		
	Chloride		
Absolute neutrophil count ^d	Creatinine		
	Glucose		
	LDH		
	Phosphorus		
	Potassium		
	Sodium		
	Total bilirubin		
	Direct bilirubin		
	Total protein		
	Uric Acid		
	Blood urea nitrogen		

^a Perform on women of childbearing potential only 72 hours prior to Day 1 of Cycle 1. All women who are being considered for participation in the trial, and who are not surgically sterilized or postmenopausal, must be tested for pregnancy within 72 hours of each cycle of trial treatment and 30 days post-treatment.

^b T3 is preferred; if not available free T3 may be tested.

^c If this test is not done as part of local standard of care, this test does not need to be performed.

^d Report % or absolute results per standard of practice. Report the results in the same manner throughout the trial.

Abbreviations: aPTT = activated partial thromboplastin time; G6PD = glucose-6-phosphate dehydrogenase deficiency; INR = international normalized ratio; LDH = lactic dehydrogenase; PT = prothrombin time; RBC = red blood cells; WBC = white blood cells.

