8.10 Subgroup Analyses and Effect of Baseline Factors

Point estimate of the ORR (with an exact two-sided 95% confidence interval) will be provided within each disease cohort. For subgroups such as age (≤ 65 vs > 65 years), sex (female vs male), race (white vs non-white) and region (US, ex-US), ORR 95% confidence interval will be provided if the subgroup sample size is adequate.

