Progressive disease ^a To be used for calculation of time to progression and progression-free survival end points for all patients including those in CR (includes primary progressive disease and disease progression on or off therapy)	Laboratory or Biochemical Relapse or Progressive Disease: requires any one or more of the following: Increase of $\geq 25\%$ from baseline in Serum M-component and/or (the absolute increase must be ≥ 0.5 g/dl) ^b Urine M-component and/or (the absolute increase must be ≥ 200 mg/24 h Only in patients without measurable serum and urine M-protein levels: the difference between involved and uninvolved FLC levels. The absolute increase must be >10 mg/dl. Bone marrow plasma cell percentage: the absolute % must be $\geq 10\%$ ^c Definite development of new bone lesions or soft tissue plasmacytomas or definite increase in the size of existing bone lesions or soft tissue plasmacytomas Development of hypercalcemia (corrected serum calcium > 11.5 mg/dl or 2.65 mmol/l) that can be attributed solely to the plasma cell proliferative disorder
Clinical relapse (i.e., progressive disease requiring re-treatment or alternate treatment) ^b	Clinical relapse or progressive disease requires one or more of: Direct indicators of increasing disease and/or end organ dysfunction (CRAB features) ^b It is not used in calculation of time to progression or progression-free survival but is listed here as something that can be reported optionally or for use in clinical practice 1. Development of new soft tissue plasmacytomas or bone lesions 2. Definite increase in the size of existing plasmacytomas or bone lesions. A definite increase is defined as a 50% (and at least 1 cm) increase as measured serially by the sum of the products of the cross-diameters of the measurable lesion 3. Hypercalcemia (>11.5 mg/dl) [2.65 mmol/l] 4. Decrease in hemoglobin of ≥ 2 g/dl [1.25 mmol/l] (see Table 3 for further details) 5. Rise in serum creatinine by 2 mg/dl or more [177 μ mol/l or more]
Relapse from CR ^a (To be used only if the end point studied is DFS) ^d	Any one or more of the following: Reappearance of serum or urine M-protein by immunofixation or electrophoresis Development of $\geq 5\%$ plasma cells in the bone marrow ^c Appearance of any other sign of progression (i.e., new plasmacytoma, lytic bone lesion, or hypercalcemia see below)

Abbreviations: CR, complete response; DFS, disease-free survival.

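### The mmol/L form of the hemoglobin entry limit in Table 1 and the hemoglobin figure in Section 12.8 rest on two unstated molar bases about fourfold apart, so the Table 1 alternative can be read as about 2 g/dL

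*Combined protocol and SAP*

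**What the plan says.** Inclusion criterion 9 refers to Table 1 (Section 5.1.2), where the hemoglobin row reads "8.0 g/dL or \geq 1.24 mmol/L". The two limits are alternatives, so meeting either is enough. Footnote a adds conditions on erythropoietin dependency and recent red-cell transfusion. A note under the table says that "laboratory value requirements should be adapted according to local regulations and guidelines for the administration of specific chemotherapies". Neither says what a mmol/L of hemoglobin means.

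Section 7.1.3.1 says that, apart from biomarker-type analyses, "all tests will be analyzed locally". The reporting unit therefore depends on the site.

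The other hemoglobin figure in mmol/L is in Section 12.8, in the reproduced myeloma criteria. Item 4 under clinical relapse is a fall in hemoglobin of at least "2 g/dl [1.25 mmol/l". The same row says of clinical relapse: "It is not used in calculation of time to progression or progression-free survival". Section 12.8 does not state a molar basis either.

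**The concern.** If the two places used the same unit, 8.0 g/dL would be four times 2 g/dL, and its mmol/L equivalent would be about four times 1.25. Table 1 instead gives 1.24, almost the figure that Section 12.8 attaches to 2 g/dL. The unit must therefore mean different things in the two places, and a reader is not told which meaning applies to the entry limit.

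This matters because the mmol/L limb stands alone as a way to qualify. A site whose laboratory reports on the Section 12.8 basis, and which follows Table 1 to the letter, would accept subjects well below 8.0 g/dL. It would record nothing unusual, because those subjects meet the criterion as written. Safety and tolerability is the trial's primary objective, and an entry limit on a blood count should mean the same at every site.

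**Working it through.** **Inputs from the documents.** Table 1: 8.0 g/dL and 1.24 mmol/L. Section 12.8: 2 g/dL and 1.25 mmol/L.

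**Step 1. Factor implied by each place (document figures only).**
- Table 1: 1.24 / 8.0 = 0.155 mmol/L per g/dL.
- Section 12.8: 1.25 / 2 = 0.625 mmol/L per g/dL.
- Ratio: 0.625 / 0.155 = 4.03.

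**Step 2. Can each pair be reproduced?** The formula is mmol/L = (g/dL × 10) / (molar mass in g/mol) × 1000. The documents give no molar mass. I assume about 64,500 g/mol for the hemoglobin tetramer, with a range of 64,000 to 65,000, and one quarter of that for the monomer.

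| Hemoglobin | Tetramer basis, mmol/L (range) | Monomer basis, mmol/L (range) |
|---|---|---|
| 8.0 g/dL | 80 / 64,500 × 1000 = 1.24 (1.23 to 1.25) | 80 / 16,125 × 1000 = 4.96 (4.92 to 5.00) |
| 2 g/dL | 20 / 64,500 × 1000 = 0.31 (0.31 to 0.31) | 20 / 16,125 × 1000 = 1.24 (1.23 to 1.25) |

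The Table 1 pair reproduces on the tetramer basis and the Section 12.8 pair on the monomer basis. Each is right on its own basis; neither is right on the other's.

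**Step 3. Cross-reading with the Section 12.8 factor (document figures only).**
- 8.0 g/dL becomes 8.0 × 0.625 = 5.0 mmol/L. If 1.25 is a rounded value between 1.245 and 1.255, the range is 4.98 to 5.02.
- 1.24 mmol/L becomes 1.24 / 0.625 = 1.98 g/dL. The same rounding gives 1.98 to 1.99.

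**Step 4. One subject, two laboratories.** Take a hemoglobin of 7.0 g/dL, below the stated 8.0.
- Section 12.8 basis: 7.0 × 0.625 = 4.4 mmol/L, above 1.24, so the mmol/L limb is met.
- Table 1 basis: 7.0 × 0.155 = 1.09 mmol/L, below 1.24, so the limb is not met.

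The same blood count qualifies or fails according to a convention that the protocol does not state.

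**The case against.** The strongest reply is that Table 1 contains no error. The pair is correct on the tetramer basis, and the g/dL figure stands beside it for anyone in doubt. That stands: a reader might infer that 1.24 mmol/L is a miscalculation, and the arithmetic does not support that. The defect is an unstated basis.

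The Section 12.8 figure is also weak as a convention for this trial. It belongs to a reproduced published table, describes a decrease, applies to myeloma only, and sits in a row for optional reporting. Inclusion criterion 12 and Section 12.7 give hemoglobin in g/dL or g/L. All of that is fair, but the figure is not needed as a convention. It shows that this document itself carries a second meaning of mmol/L for hemoglobin.

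A reader might go further and infer that the floor falls to about 2 g/dL at every site using mmol/L. The documents do not support this. It requires a site that reports mmol/L, does so on the monomer basis, and applies 1.24 despite the adjacent 8.0 g/dL. None of the three is established. The planned subgroup by "region (US, ex-US" suggests sites outside the US but says nothing about laboratory units. The local-adaptation note does not settle the basis either, since it concerns regulations and guidelines for specific chemotherapies.

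A reader might also infer that this limit is the main protection against anemia and that the ambiguity biases the safety results. Table 8 does give start-of-cycle rules for neutrophils and platelets and none for hemoglobin. But entry also depends on the transfusion and erythropoietin conditions, ECOG status 0 or 1 and a judgement of cardiac function; blood counts are scheduled on Days 1 and 8; and adverse event review looks for new or worsening events. No figure shows excess anemia attributed to treatment. The bias claim is not demonstrated.

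**Conclusion.** The point holds as an ambiguity in a printed eligibility limit. The protocol expresses hemoglobin in mmol/L on two unstated bases that differ by a factor of 4.03. On the Section 12.8 basis, the mmol/L alternative in Table 1, read literally, corresponds to about 1.98 g/dL, which does not match the stated 8.0 g/dL. Both figures rest on document numbers alone. The statement that Table 1 is consistent on a tetramer basis rests on the assumed molar mass of 64,000 to 65,000 g/mol.

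The practical consequence is conditional on local laboratories reporting on the monomer basis. The documents do not show that any do, so the number of subjects affected cannot be given. The range from about 2 to below 8.0 g/dL is a bound on what the wording permits, not an estimate of who was enrolled. The prospective effect is limited: the rrMM and rrCLL cohorts are closed to enrollment, which leaves at most rrDLBCL entry.

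**What to change.** Reconcile Table 1 with Section 12.8 in one of two ways: delete the mmol/L alternative in Table 1, or keep it and name its molar basis so that both limbs express the same stated limit. Neither changes the limit the protocol already gives in g/dL.

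For subjects already enrolled, ask which sites report hemoglobin in mmol/L and on what basis. For those sites, list screening hemoglobin converted to g/dL and flag values below the stated 8.0 g/dL for the safety review. Do not class these subjects as protocol deviations, because they met the criterion as written.

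The cost is one table cell in an amendment or clarification letter, a query to the sites concerned, and one listing from data already held. No new tests are needed.
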